6.9 Recommendations before and after invasive procedures and surgical intervention

If an invasive procedure or surgical intervention is required, rivaroxaban should be stopped at least 24 hours before the intervention, if possible and based on the clinical judgment of the physician. If the procedure cannot be delayed, the increased risk of bleeding should be assessed against the urgency of the intervention. Rivaroxaban should be restarted after the invasive procedure or surgical intervention within 24 hours, provided the clinical situation allows and adequate hemostasis has been established.

6.10 Management of bleeding in children

If a child has a serious bleed during study treatment, the following routine measures could be considered:

- Consider usual treatment for bleeding, including blood transfusion, and/or fresh frozen plasma.
- Obtain PK/PD blood sample.
- If bleeding cannot be controlled, consider administration of one of the following procoagulants:
 - 4-factor prothrombin complex concentrate
 - recombinant factor VIIa (NovoSeven[®])
- Protamine sulfate and vitamin K are not expected to affect the anticoagulant activity of rivaroxaban.

6.11 Efficacy outcome

The efficacy outcome will be the composite of all symptomatic recurrent thromboembolism and asymptomatic deterioration in thrombotic burden on repeat imaging.

6.12 PK/PD assessment - amended

Blood samples will be taken for PK/PD measurements. The number and volume of PK/PD blood samples represents the minimum amount of blood needed for adequate analysis (sparse sampling approach). The following blood samples will be taken: ⁴⁷

- two post-dose PK samples at visit 2
- one post-dose PD sample at visit 2
- two post-dose PK sample at visit 3
- one post-dose PD sample at visit 3
- one post-dose PD sample at visit 4

The exact time of rivaroxaban dosing and PK/PD blood sampling will be documented in the eCRF. If, for any reason, PK/PD samples are taken outside of the pre-specified time window, the exact time that the sample was taken should be recorded and not the time of the time window.

The use of low dose heparin and tissue plasminogen activator to maintain catheter patency is acceptable. However before collecting PK/PD samples, the catheters need to be flushed with saline. In addition, if PK/PD samples are drawn through a central line, a small amount of blood needs to be drawn and discarded, before collecting the PK/PD sample in order to avoid dilution of the PK/PD sample with saline that remains in the central line.

The prothrombin time, activated partial thromboplastin time and anti-factor Xa activity (anti Xa) will be used to assess the pharmacodynamic effects after administration of the study drug.

Detailed information about the handling and labeling of the samples will be provided in the laboratory manual.

The data obtained from the blood samples taken will be analyzed.

6.13 Study booklet

Parents will receive a booklet with the following information:

- The local medical contact person and emergency telephone number
- The visit schedule, including dates of telephone and/or hospital visits
- Instructions to keep empty, partially used, and unused bottles of study medication
- Instructions on signs and symptoms of bleeding
- How to take rivaroxaban

⁴⁷ This section was modified via Amendment 5 (see Section 16.3.2.9)

6.14 Study committees

6.14.1 Steering committee

The steering committee has the overall scientific responsibility of the study. Its tasks and responsibilities are:

- To facilitate and approve the final protocol
- To help select the investigators network
- To support and organize the national logistics in the initiation and conduct of the study
- To ensure a scientifically sound and safe conduct of the study
- To decide on the DMC recommendations
- To guarantee the integrity of data collection and analyses
- To monitor progress of study enrollment
- To assist in the analysis and presentation of the results
- To decide on the publication and presentation policy of final results

6.14.2 Central independent adjudication committee (CIAC)

All index venous or arterial thrombotic events, and all suspected recurrent thromboembolic events, asymptomatic deterioration in the thrombotic burden on repeat imaging, bleeding, other vascular events and deaths that occur after visit 2 including the 30-day post treatment period will be evaluated by a CIAC, which will be provided with all relevant documentation related to the events. The procedures followed by the CIAC will be described in an adjudication manual. Adjudication results will be the basis for the final analyses.

6.14.3 Data monitoring committee (DMC)

This committee has the responsibility to provide the steering committee with recommendations related to the protection of the children's safety, including stopping recruitment and study treatment. For that purpose, the DMC will regularly review all incidences of serious adverse events, recurrent venous or arterial thromboembolic events and bleeding. Organizational aspects, responsibilities, and processes will be described in the DMC charter.

7. Statistical and analytical methods

7.1 General considerations

The plan described in the following sections will be detailed in a statistical analysis plan (SAP). The SAP will accommodate protocol amendments or unexpected issues in study execution or data that affect planned analyses. Any revision will be clearly identified in the final SAP, issued prior to data base lock. If not stated otherwise, the following statistical specifications will apply.

7.2 Analysis sets

Full analysis set:	This analysis set will include all children from whom informed consent was obtained.
Safety analysis set:	This analysis set will include all children who received at least one dose of rivaroxaban.
Per protocol analysis set:	This population includes all children who completed the 7-day treatment period or had an efficacy or bleeding outcome before. This analysis set may exclude major protocol deviations.
Listing only set:	This population includes all screening failures.

7.3 Demographic and other baseline characteristics

Summary statistics (arithmetic mean, standard deviation, median, minimum and maximum for quantitative variables) will be presented. Frequency tables for qualitative data will be provided. Medical history findings will be summarized using Medical Dictionary for Regulatory Activities (MedDRA) terms.

7.4 Safety analysis

All safety analyses will be performed on the safety population. The analysis will primarily focus on bleeding that occurred during or within 2 days after stop of rivaroxaban. Bleeding events observed later will be described separately. Individual listings of major and clinically relevant non-major bleeding will be provided. The incidence of bleeding will be summarized. If a sufficient number of bleeding events is observed, factors which potentially influence the occurrence of bleeding will be assessed by appropriate statistical procedures. Quantitative data will be described by the summary statistics and will be presented for the original data as well as for the difference to baseline. Frequency tables will be provided for qualitative data.

7.5 Efficacy analysis

All efficacy analyses will be performed on the full analysis set population. The incidence of symptomatic recurrent venous thromboembolism and asymptomatic deterioration in thrombotic burden on repeat imaging will be summarized.

7.6 PK/PD analysis

PK/PD modeling, using population approaches will be used to describe the pharmacokinetics of rivaroxaban, and to relate anticoagulant parameters of rivaroxaban with plasma concentrations.

7.7 Interim analyses

No interim analysis will be performed.

7.8 Determination of sample size

At least 8 children are planned to be enrolled in the study. For the area under the curve (AUC), a geometric coefficient of variation (geom. CV) of about 40% was observed in adults, and was also observed in study 12892 in the age group 12 to 18 years (n=9). In the age cohort 6 to <12 years, an even smaller geometric coefficient of variation was observed. Although it is expected from the model that the variability will be higher in neonates and infants, the exact numbers remain unclear. The sample size of 8 subjects will yield an exploratory 90% confidence interval for the geometric mean AUC-estimate between 50% and 200% of the estimate, provided the geometric coefficient of variation does not exceed 138%, which would be more than a tripling of the variability observed in adolescents. If the geometric coefficient of variation will be 80%, the exploratory 90% confidence interval for the geometric mean AUC-estimate would be located between 62% and 161% of the estimate.

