	
4. Oral feeding/nasogastric/gastric feeding for at least 10 days.
 
5. Informed consent provided.
 
6. Body weight >2600 g.⁹
 
Exclusion
 
1. Active bleeding or high risk for bleeding contraindicating anticoagulant therapy, including history of intra-ventricular bleeding
 
2. Symptomatic progression of thrombosis during preceding anticoagulant treatment
 
3. Planned invasive procedures, including lumbar puncture and removal of non-peripherally placed central lines during study treatment
 
4. Hepatic disease which is associated with either: coagulopathy leading to a clinically relevant bleeding risk, or alanine aminotransferase (ALT) > 5x upper level of normal (ULN) or total bilirubin (TB) > 2x ULN with direct bilirubin > 20% of the total
 
5. Creatinine > 1.5 times of normal
 
6. Uncontrolled hypertension defined as > 95th percentile^a ¹⁰
 
7. History of gastrointestinal disease or surgery associated with impaired absorption
 
8. Platelet count <100 x 10⁹/L
 
9. Concomitant use of strong inhibitors of both cytochrome P450 isoenzyme 3A4 (CYP3A4) and P-glycoprotein (P-gp), e.g. all human immunodeficiency virus protease inhibitors and the following azole-antimycotics agents: ketoconazole, itraconazole, voriconazole, posaconazole, if used systemically (fluconazole is allowed) ¹¹
 
10. Concomitant use of strong inducers of CYP3A4, e.g. rifampicin, rifabutin, phenobarbital, phenytoin and carbamazepine ¹²
 
11. Indication for anticoagulant therapy other than current thrombosis
 
12. An indication for continued antiplatelet therapy or non-steroid anti-inflammatory drug (NSAID) therapy. Incidental use is allowed. ¹³
 
13. Hypersensitivity to rivaroxaban or its excipients
 
14. Participation in a study with an investigational drug or medical device within 30 days prior to enrollment.
 
^a See Appendix 17.1.2

Study design	Non-randomized, open label, multicenter, combined single and multiple dose study

⁹ Inclusion criterion 6 was added via Amendment 1 (see Section 16.1.2.1)

¹⁰ Exclusion criterion 6 was modified via Amendment 4 (see Section 16.2.2.2)

¹¹ Exclusion criterion 9 was modified via Amendment 1 (see Section 16.1.2.1)

¹² Exclusion criterion 10 was modified via Amendment 1 (see Section 16.1.2.1)

¹³ Exclusion criterion 12 was modified via Amendment 4 (see Section 16.2.2.2)

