1.3 Rationale of the study and risk-benefit assessment - amended

Treatment options are limited to heparins and VKA, which are cumbersome to manage due to the requirement for daily subcutaneous or intravenous injections and regular blood sampling for laboratory monitoring followed by dose adaptations. In children, the availability of an oral anticoagulant treatment that does not require subcutaneous or intravenous injections and regular blood sampling for laboratory monitoring, as is the case in adults, would be desirable.

In adults, rivaroxaban is administered orally and is characterized by stable and predictable pharmacokinetics and, therefore, does not require laboratory monitoring with subsequent dose adjustments. In the Phase III EINSTEIN DVT and PE studies in adults,⁽⁹⁾ rivaroxaban was non-inferior to standard of care with enoxaparin followed by VKA treatment. In the pooled analysis, the incidence of the primary efficacy outcome (the composite of symptomatic

¹⁹ The heading was modified via Amendment 4 (see Section 16.2.2.4)

recurrent DVT, non-fatal and fatal PE) was lower on rivaroxaban than on enoxaparin/VKA treatment, with a similar incidence of clinically relevant bleeding. The comparison against placebo in patients studied for extended treatment of VTE (EINSTEIN extension study) demonstrated clear superiority for rivaroxaban against placebo in all efficacy analyses and across all subgroups. Rivaroxaban was well tolerated and the safety profile, including adverse events and observed laboratory abnormalities, was comparable to enoxaparin/VKA treatment.

As a consequence, the expectation is that the selected rivaroxaban age- and body-weight adjusted dose regimen in children will be safe and efficacious without the need for frequent blood sampling to monitor the anticoagulant activity.

To carefully allow for the evaluation of rivaroxaban in neonates and children younger than 6 months with confirmed symptomatic or asymptomatic arterial or venous thrombosis, we elected to evaluate the selected rivaroxaban dose regimen first in children that have been treated with anticoagulant therapy for at least five days. If this study reveals that the selected rivaroxaban dose regimen results in a similar exposure as that observed with 20 mg rivaroxaban in adults, and safety and efficacy is confirmed, a subsequent study will evaluate the selected rivaroxaban dose regimen for the acute and continued treatment of VTE. ²⁰

2. Study objectives

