4.1 Planned number of children

At least eight children are planned to be enrolled in the study.

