5.1 Method of treatment allocation

5.1.1 Rivaroxaban regimen - amended

Age- and body weight-adjusted rivaroxaban will be administered three times daily approximately 8 hours apart as oral suspension. The oral suspension will be administered immediately before or (early) during feeding.³¹

Originally, the study started with a b.i.d. regimen. Rivaroxaban was well tolerated in the 5 children treated according to the b.i.d. regimen and there were no bleeding events. Furthermore, no symptomatic recurrent venous thromboembolic complications occurred. Repeat imaging of the thrombosis in two children with a persistent thrombosis at the start of

²⁷ Exclusion criterion 9 was modified via Amendment 1 (see Section 16.1.2.3)

²⁸ Exclusion criterion 10 was modified via Amendment 1 (see Section 16.1.2.3)

²⁹ Exclusion criterion 12 was modified via Amendment 4 (see Section 16.2.2.9)

³⁰ This section was modified via Amendment 4 (see Section 16.2.2.10)

³¹ Throughout the complete section t.i.d. dosing was introduced via Amendment 5 (see Section 16.3.2.5)

rivaroxaban treatment showed normalization and substantial regression of the thrombosis, respectively, after the 7-day treatment with rivaroxaban.

However, PK results of the first 5 children enrolled with the b.i.d. regimen indicate lower rivaroxaban exposure ($AUC_{ss,24h}$) and C_{trough} concentrations than initially expected by the PK model. Based on these observations, the Data Monitoring Committee recommended to change the dosing regimen from a b.i.d. (approx. 12-hour intervals) to a t.i.d. (approx. 8-hour intervals) schedule applying the same individual doses previously administered twice daily. This recommendation was endorsed by the steering committee.

Following implementation of Amendment 5, children will be dosed according to the t.i.d. schedule (according to [Table 3](#)). The 50% increase of the total daily dose will increase the exposure, and the shortening of the dosing interval from 12 to 8 hours (t.i.d. schedule) aims to increase the C_{trough} concentrations.

If a rivaroxaban individual dose was missed, the t.i.d. administration schedule with approx. 8-hour intervals should be resumed without compensating for the missed dose.

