16.3.1.3 Change 3: Modification of dosing regimen

The total daily dose will be increased by 50% for all body weight groups. This will be achieved by three times daily administration of the same individual dose previously used with the b.i.d. schedule.

Rationale:

Rivaroxaban was well tolerated in the 5 children treated according to the b.i.d. regimen and there were no bleeding events. Furthermore, no symptomatic recurrent venous thromboembolic complications occurred. Repeat imaging of the thrombosis in two children with a persistent thrombosis at the start of rivaroxaban treatment showed normalization and substantial regression of the thrombosis, respectively, after the 7-day treatment with rivaroxaban.

However, PK results of the first 5 children enrolled with the b.i.d. regimen indicate lower rivaroxaban exposure ($AUC_{ss,24h}$) and C_{trough} concentrations than initially expected by the PK model.

Based on these observations the Data Monitoring Committee in its meeting on September 19, 2016, identified an efficacy concern. The DMC clarified that “the efficacy concern the committee identified was related to the potential for the low levels to be associated with thrombotic events, not related to any observed events in the patients treated to date.” The DMC recommended to change the dosing regimen from a b.i.d. (approx. 12-hour intervals) to a t.i.d. (approx. 8-hour intervals) schedule, applying the same individual doses previously administered twice daily. This recommendation was endorsed by the steering committee.

The 50% increase of the total daily dose aims to elevate the exposure to the lower end of the adult reference range. The shortening of the dosing interval from 12 hours (b.i.d. schedule) to 8 hours (t.i.d. schedule) aims to increase the C_{trough} concentrations to match the adult reference range which will allow to extrapolate safety and efficacy from the adult VTE treatment population.

The change from b.i.d. to t.i.d. schedule requires an adaptation of PK/PD sampling timepoints and instructions for administration of rivaroxaban.

The original protocol included dosing information for children with body weight of 12 to < 20 kg. This specific dosing information was deleted as this body weight group does not apply to children aged younger than 6 months.

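### The n=8 precision in Protocol 7.8 was not updated after Amendment 5 and is not assured for 24-hour AUC on the current t.i.d. regimen

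*Protocol*

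**What the plan says.** **Sample size.** Protocol 7.8: "The sample size of 8 subjects will yield an exploratory 90% confidence interval for the geometric mean AUC-estimate between 50% and 200" percent of the estimate, provided the gCV does not exceed 138%; at gCV 80% the interval is given as 62% to 161%. The reference gCV is about 40% (adults and adolescents), and 7.8 expects a higher value in this age group. It speaks only of AUC, although the Synopsis calls the trial a "combined single and multiple dose study". Protocol 4.1: "At least eight children are planned to be enrolled in the study".

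**Regimen change.** Protocol 5.1.1: "PK results of the first 5 children enrolled with the b.i.d. regimen indicate lower rivaroxaban exposure". It names steady-state 24-hour AUC and trough concentration as the quantities that fell short. The regimen became t.i.d., "applying the same individual doses previously administered twice daily", and "The 50% increase of the total daily dose will increase the exposure".

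**Purpose.** Protocol 1.3 plans a subsequent study if "the selected rivaroxaban dose regimen results in a similar exposure as that observed with 20 mg rivaroxaban in adults" and safety and efficacy are confirmed. The rationale in 16.3.1.3 says: "The 50% increase of the total daily dose aims to elevate the exposure to the lower end of the adult reference range". It sets a second aim of matching the adult range for trough concentrations.

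**Analysis.** Protocol 7.6 plans population PK/PD modelling and is silent on regimen. The SAP (section 1) rests on protocol version 2.0 and describes b.i.d. dosing only. SAP 5.1 defines one PK analysis set, and SAP 6.4 lists geometric means and geometric SDs but no confidence interval. Protocol 7.1 says the SAP will take account of amendments.

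**The concern.** A precision statement for eight children needs eight children who estimate the same mean. For 24-hour AUC that stopped being true with Amendment 5, because the protocol itself says the higher daily dose raises exposure. Yet neither 4.1 nor 7.8 is among the sections that the amendment lists as affected by the regimen change, and neither heading is marked as amended. No minimum number of t.i.d. children is set, and nothing says whether the five b.i.d. children count toward the eight.

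The quantity closest to the question in 1.3 is exposure under the regimen now in use. The amendment aims only at the lower end of the adult range for AUC, so the width of the interval around t.i.d. exposure bears on what the trial can claim. A reader who takes 62%-161% as the precision for t.i.d. 24-hour AUC may be relying on more information than the plan assures.

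**Working it through.** **Inputs.** 90% interval, n=8, limits 50%-200%, gCV 40%, 80% and 138% (7.8); five b.i.d. children and a daily dose ratio of 1.5 (5.1.1); at least eight in total (4.1).

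**Formulas.** With log-normal AUC, σ = √ln(1 + gCV²). The interval runs from 1/f to f times the geometric mean, where f = exp(t(0.95, df)·σ/√n). The largest gCV that keeps the interval within 50%-200% is √(exp[(ln 2·√n / t)²] − 1).

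**Step 1: reproduce 7.8.** n=8, df=7, t=1.895.
- gCV 80%: σ = √ln 1.64 = 0.703; f = exp(1.895 × 0.703/2.828) = 1.602, so 62.4%-160.2%. The stated 161% is the reciprocal of the rounded 62%.
- Limit: (0.693 × 2.828/1.895)² = 1.071; √(e^1.071 − 1) = 1.385, so 138%.

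Both figures in 7.8 are confirmed.

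**Step 2: t.i.d. children assured.** 8 − 5 = 3, if all five b.i.d. children count, no further child started on b.i.d., and enrolment stops at eight.

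**Step 3: same interval, t.i.d. data alone.** For n=3, df=2, t=2.920: f = exp(2.920 × 0.703/1.732) = 3.27.

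| t.i.d. children | 90% interval at gCV 80% | gCV limit for 50%-200% |
|---|---|---|
| 3 | 31%-327% | 43% |
| 4 | 44%-229% | 64% |
| 5 | 51%-196% | 83% |
| 6 | 56%-178% | 102% |
| 8 | 62%-160% | 138% |

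At the adult gCV of 40%, three children give 52%-191% and eight give 77%-129%.

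**Step 4: three t.i.d. children, log-variance pooled over both regimens.** df = (5 − 1) + (3 − 1) = 6, t=1.943. At gCV 80%, f = exp(1.943 × 0.703/1.732) = 2.20, so 45%-220%; the limit is 68%.

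**Step 5: what can still use all eight.** The amount per administration is unchanged within a weight band, so clearance (CL/F) or per-dose AUC can be common to both regimens. If it is, precision of up to about the n=8 level applies to that quantity, and t.i.d. 24-hour AUC can be derived from it as daily dose divided by CL/F. This needs linear PK, and any regimen or formulation effect must be absent or modelled. Neither document states these conditions.

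**Step 6: why 24-hour AUC should not be summarised over both regimens together.** Under linear PK the b.i.d. value is the t.i.d. value divided by 1.5. The geometric mean over five b.i.d. and three t.i.d. children is then 1.5^(−5/8) = 0.776, about 78% of the t.i.d. value.

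**The case against.** The strongest reply is that the widest interval comes from an analysis that nobody plans. Sampling is sparse (6.12), and PK is to be described by population modelling (7.6; SAP 6.4 summarises model-derived characteristics if applicable). In such a model the b.i.d. children inform clearance, and a regimen or formulation effect can be estimated, although with few children. This stands: the interval from three children alone is the minimum case, not a forecast. It does not remove the gap, because the pooling conditions are unstated. Amendment 4 also replaced the ready-to-use suspension with granules (16.2.1.6), and the documents do not say which formulation each b.i.d. child received. That section offers partial support for the granules: a relative bioavailability test in adults, and PK from 16 children that agreed with model predictions. Those children were at least 6 months old, and in the present age group the first five had lower exposure than the model expected.

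Three is also a floor. The plan says at least eight, and five t.i.d. children already bring the interval within 50%-200% at gCV 80%. This stands too.

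The SAP lacks a regimen split because it was written when only b.i.d. existed, and 7.1 foresees its revision. The absent split is therefore work for that update, not a separate error. Nor does the SAP expressly plan one geometric mean of 24-hour AUC across regimens; its single PK set merely does not prevent it.

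**Conclusion.** The sample-size statement was not carried through an amendment. A reader might infer that 7.8 is miscalculated; it is not, since both its figures reproduce. A reader might also infer that the trial will have only three t.i.d. children, or that t.i.d. exposure will be known only to within 31%-327%. The documents support neither: three is the least the plan assures, and the planned model can use all eight children.

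What holds is narrower. The n=8 precision is not assured for t.i.d. 24-hour AUC. It applies if eight t.i.d. children are enrolled, or to a regimen-independent quantity under conditions that the plan does not state. On t.i.d. data alone the gCV limit falls from 138% to 43% in the minimum case, just above the adult 40%, while 7.8 expects higher variability here. With borrowed variance it is 68%.

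The size is minor to moderate. The interval is exploratory, no decision rule uses it, and extrapolation from adults also rests on trough concentrations. The figures assume log-normal AUC and, where variance is borrowed, equal log-variance in both regimens. The minimum case assumes that the five count and enrolment stops at eight; the 78% figure also assumes linear PK.

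**What to change.** 1. In 7.8, name the AUC and do one of two things. (a) Restate the precision for t.i.d. steady-state AUC(0-24) over the possible numbers of t.i.d. children, with three as the minimum case, with and without borrowed b.i.d. variance. (b) Limit the n=8 figure to CL/F or per-dose AUC from the population model, and state the pooling assumption: linear PK, with any regimen or formulation effect absent or modelled. Mention the Amendment 4 formulation change there.
2. In 4.1, say how the five b.i.d. children count toward the eight.
3. In the SAP update foreseen in 7.1, summarise model-derived steady-state AUC(0-24) and trough concentration by regimen. Give the geometric mean and 90% confidence interval for the t.i.d. children against the adult reference range. Do not summarise 24-hour AUC over both regimens together.

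The cost is wording in two protocol sections and a by-regimen table in an SAP that has to be revised anyway. No extra enrolment is needed. The drawback is a less favourable stated precision under (a), or open reliance on a pooling assumption under (b).
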